10. AUDIO/VIDEO RECORDINGS

The CBT-TS intervention sessions and the study assessments will be video recorded on Zoom. The recordings will be converted from Zoom and directly transferred to a folder on Box.com, a secure server hosted at URMC, for storage. The recordings will be used for supervision and monitoring of the intervention delivery, data storage, verification, and data analysis. Only IRB-approved study personnel will have access to the video recordings stored on Box.com.

11. RISKS TO SUBJECTS

The proposed study procedures pose minimal risks to subjects. The information below that describes the risks associated with the study interventions was taken from the IRB approved protocol and consent form.

- a. **Assessment sessions (i.e., screening, baseline, and follow-up):** For the assessment sessions, the risks are as follow: mild reactions of distress or fatigue, identification of suicide ideation, invasion of privacy, or breach to confidentiality (if safety issues are detected). Subjects are not required to answer any questions posed during the study

and they may withdrawal from the study at any time without consequences. Subjects may request breaks if needed during the study or may request to stop at any time. Study personnel have specialized training in working with Deaf individuals who have behavioral health problems and are capable of providing support as needed. All of the assessment measures and the assessment procedures were safely used in my URMC IRB approved pilot study with Deaf individuals. No sustained negative effects from the assessments are expected, but negative outcomes cannot be ruled out. There is a slight risk that research data files might be compromised and obtained or viewed by unauthorized persons. Our procedures for protecting against such risks are described below.

- b. **Intervention Sessions:** For the intervention sessions, the risks are as follow: subjects may experience mild reactions of distress or fatigue during the sessions if they recall past negative experiences attempting to seek treatment. Subjects will receive support from the interventionist for such experiences. In addition, due to the real barriers encountered by Deaf individuals when trying to access mental health or substance abuse treatment, it is possible that subjects who decide to seek treatment may not be able to access services or may have negative experiences in treatment. The intervention has features to address this possibility, including an optional second session with the interventionist to identify appropriate treatment options, problem-solve barriers to accessing treatment, and scheduling a treatment session. In addition, subjects will be provided with a list of multiple Deaf treatment resources, services for identifying treatment resources in their area, and accessible crisis counseling services (i.e., video phone and texting). No sustained negative effects are expected from the intervention sessions, but negative outcomes from behavioral interventions cannot be ruled out.

Adequacy of Protection Against Risks:

Protections Against Risk:

- a. **Confidentiality:** In order to protect the confidentiality of subject information, we will take a number of precautions. These include training study personnel in confidentiality procedures; entry and storage of data using coded identification labels; separate storage of identifying information; use of URMC, encrypted, project laptops with restricted access by enforced password protection; and use of HIPAA compliant data management software (REDCap and Box.com). All data, including assessment measures, will be obtained with the written consent of the patient. Information pertaining to individual subjects will be released with the subject's informed and written consent only, except in unusual cases where withholding the information might pose a serious risk or danger to the subject or others. All data collection involving human subjects will be HIPAA compliant. Assessment data collected for this study will be entered into REDCap, a software toolset and workflow methodology for electronic collection and management of research data. REDCap was created specifically around HIPAA-Security guidelines including a full audit trail, user-based privileges, and integration with institutional servers. A unique study number will be assigned to each subject and all records pertaining to a given individual will be linked via this identification number. The databases will be password protected and access will be limited to relevant research personnel. All subject identification data (e.g., names, identification number, email address, video phone numbers, etc.) will be separated from the research data and stored securely in a separate folder on Box.com. Subject identification data will be used to contact enrolled subjects for scheduling, appointment reminders, or follow-up. Only IRB-approved

investigators with a need for access will have access to subject data. All paper copies of the assessment forms and notes from the intervention and follow-up interview sessions will be stored in a locked file cabinet in the PI's locked office in the Department of Psychiatry at URMC.

The assessment and intervention sessions will be video recorded on Zoom. Research personnel will use a licensed URMC Zoom account which protects and encrypts all audio, video, and screen sharing data and supports HIPPA compliance. Subjects participating in the assessment and intervention sessions will be sent unique Zoom links for entering the Zoom meetings. Research personnel will use the waiting room feature to control subject access to the sessions and will lock the meetings after the subject joins the session. Following the sessions, the recordings will be directly uploaded to password protected drives on Box.com for secure storage. The recordings will be accessible only by IRB approved study personnel at URMC.

Publications or presentations resulting from this study will report only cumulative data or descriptions certain to maintain subjects' anonymity. Lastly, to minimize social and legal risks, this study contains a Certificate of Confidentiality to protect subjects' information. An explanation of the Certificate of Confidentiality is included in the informed consent form

- b. Identification of suicide ideation: Subjects will be screened for suicidal ideation using the PHQ-9, item 9. Subjects who endorse suicidal ideation will be administered a structured, validated follow-up assessment (P-4 Screener). Subjects who score as "high risk" on the P-4 Screener will be excluded from the study. Upon identification of a high risk for suicide, study personnel will provide support to the individual and contact the PI, [name], a licensed clinical psychologist with specialized training in working with Deaf individuals, including those at high risk for suicide, and [name] [name], a licensed clinical psychologist and expert in the prevention and treatment of suicide. Together, the team will take appropriate actions to reduce the individual's risk for suicide, including developing a safety plan, contacting treatment professionals, friends, family members, and/or emergency services if needed, and referring the individual to mental health services.
- c. Subject distress: Risks associated with subject burden or distress will be minimized by employment of research personnel with appropriate background and experience with psychological factors and Deaf subjects. Study personnel have specialized training in working with Deaf individuals who have behavioral health problems and are capable of providing support as needed throughout the study to manage mild to moderate reactions of distress that may arise. In the rare situation that a subject experiences a more severe reaction of distress during the course of the study, study personnel will evaluate the subject's emotional state and safety. Study personnel will briefly attempt to de-escalate the patient's distress. If these measures do not effectively reduce the patient's distress within 10-15 minutes and depending on the severity of the patient's distress, study personnel will contact the PI and the PI's mentor, [name] [name]. Together, the team will take appropriate actions to reduce the individual's risk for suicide, including developing a safety plan, contacting treatment professionals, friends, family members, and/or emergency services if needed, and referring the individual to mental health services.

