8. CONSENT PROCESS

Prior to the screening assessment, interested subjects will be provided with an overview of the study goals and an in-depth explanation of the procedures for the screening assessment. Subjects will give verbal consent via Zoom to participate in the screening

assessment, and this consent will be documented by study personnel in REDCap (Research Electronic Data Capture), a HIPPA-compliant, secure, web-based application designed exclusively to support data capture for research studies. REDCap is hosted locally by URMC and employs user authentication and role-based security. The REDCap application resides in an isolated secure network segment designed for personal health information, personally identifiable information, and other types of regulated data. At the completion of the screening assessment, subjects who are eligible to participate in the study will be invited to participate in the written informed consent process for enrollment in the study.

Electronic, written informed consent will be obtained directly from eligible subjects via Zoom. An IRB-approved e-Consent form will be created using a REDCap-based electronic form. Potential subjects will participate in the consent process by accessing the e-Consent form via a link provided to them through e-mail. The study personnel will request verbal permission to send the e-Consent via email. The request will state "Because URMC can't control the security of email once we send them, we need your permission to email you. Do you want to receive the link to the e-Consent via email?" The email will not include PHI. To authenticate the identity of the individual signing the e-Consent form, the study personnel and the subject will agree on a passcode for accessing the e-Consent form. This passcode will be saved as part of the subject's record for verification use. Through the use of a "Survey Login" feature, an individual will be prompted to enter the passcode to grant entry to the e-Consent form. The entered passcode will be matched against the stored version entered by study staff for that subject. A matching response will grant entry to the e-Consent and non-matching responses will block the individual based on specified settings.

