9. STUDY PROCEDURES

Screening Procedures: Recruitment materials will direct individuals to contact the research team via email or video phone to schedule a screening assessment with study personnel on Zoom. We will use procedures for screening that were successful in the PI's postdoctoral pilot study conducted at URMC. During the screening assessment, study personnel will briefly review the overall study goals and then explain the screening procedures to interested subjects. Study personnel will obtain verbal consent from interested subjects prior to proceeding with the screening assessment. This verbal consent will be documented in REDCap.

Subjects will be screened for eligibility using a (1) brief demographic survey, (2) several behavioral health measures including: the 10-item Alcohol Use Disorders Identification Test (AUDIT) to screen for AUD, 4-items from the National Survey of Drug Use and Health (NSDUH; Center for Behavioral Health Statistics and Quality, 2015) to determine if alcohol use within the past 30 days exceeds the limits for low-risk drinking adopted by NIAAA, the Patient Health Questionnaire-9 (PHQ-9) to screen for symptoms of depression, the Generalized Anxiety Disorder 7-item Scale (GAD-7) to screen for symptoms of anxiety, the PTSD Checklist for DSM-5 (PCL-5) to screen for symptoms of PTSD, and the Insomnia Severity Index (ISI) to screen for symptoms of sleep disturbance, and (3) screening items on the Alcohol Use Disorders and Associated Disabilities Interview (AUDADIS) to determine if there is any history of or current engagement in professional alcohol or mental health treatment.

The screening will begin with the demographics survey and then proceed to the behavioral health measures if the subject is eligible. The behavioral health measures will be administered to subjects in the order listed (see Sources of Research Materials below) until the subject screens positive on one of the measures. If the subject screens positive on one of the behavioral health measures, they will skip to the treatment engagement screening questions. If the subject does not screen positive on any of the behavioral health measures,

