they will be informed that they are not eligible for the study. Study personnel will share their screen with the measure items presented in written English and record the subjects' responses on paper forms. At the completion of the screening assessment, data from these paper forms will be manually transferred to REDCap, and the paper forms will be stored in a locked cabinet in the PI's locked office in the Department of Psychiatry at URMC. Study personnel will be present to clarify any items or translate the items to ASL if requested by the subject. The screening appointment should last approximately 25 – 40 minutes depending on the number of measures administered (e.g., if the subject screens positive early in the screening process or not), the subject's experience with research, and their fluency in English. Eligible and interested subjects will proceed to complete the written informed consent process for enrollment in the study.

Baseline Assessment: After completing the informed consent process, subjects will schedule a baseline assessment appointment with study personnel on Zoom. The baseline assessment will follow the same general procedures as the screening assessment. The baseline assessments will consist of a full demographics survey, administration of any remaining behavioral health measures, and the Deaf Perceptions About Services Scale (D-PASS). The baseline assessment appointment should last approximately 35 minutes – 1 hour. After completing the baseline assessment, subjects will schedule their intervention session with the interventionist.

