17. DATA AND SAFETY MONITORING PLAN

Safety Monitoring: Given that this study presents no more than minimal risk, data and safety monitoring will be the responsibility of the study PI, in consultation with the PIs' mentoring team. Individual subject data will be monitored by the PI and study personnel over the course of the study to identify any subjects who may need additional support. Alcohol use, and symptoms of post-traumatic stress disorder (PTSD), depression, suicidal risk, anxiety, and insomnia will be assessed at screening, baseline, and one-month follow-up assessments. If at any time a subject is identified by study personnel or the PI as having a serious psychiatric or alcohol use problem that requires immediate and intensive treatment (i.e., danger to self or others), this concern will immediately be reported to the PI and the PI's primary mentor, who will provide support, referral, and bridging to appropriate treatment options for stabilization. Should a subject present at a study session under the influence of drugs or alcohol, study personnel will be trained to discontinue the session, reschedule the session for a later date, and work with the subject to ensure they are in a safe place (i.e., at home, with family or friends, etc.). Should a subject communicate distress and intent to withdraw from the study, the PI will provide the subject with a list of

Deaf treatment resources to help the individual locate possible treatment options in their area.

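### On the order listed in Section 9, a subject who screens positive for alcohol use disorder is enrolled before the suicide-risk exclusion can act, and nobody is checked at both screening and baseline as Section 17 says

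*Combined protocol and SAP*

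**What the plan says.** All references are to the combined protocol and SAP.

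- **Section 11, identification of suicide ideation.** PHQ-9 item 9 is the trigger, an endorsed item leads to the P-4, and subjects rated high risk "on the P-4 Screener will be excluded from the study". No visit is named.
- **Section 9, screening.** "The behavioral health measures will be administered to subjects in the order listed", with a pointer to a later list. The prose list starts with "the 10-item Alcohol Use Disorders Identification Test (AUDIT) to screen for AUD", then gives four past-30-day alcohol items, the PHQ-9, GAD-7, PCL-5 and ISI. "If the subject screens positive on one of the behavioral health measures, they will skip to the treatment engagement screening questions".
- **Section 8.** At the end of screening, "subjects who are eligible to participate in the study will be invited to participate in the written informed consent process".
- **Section 9, baseline.** "After completing the informed consent process, subjects will schedule a baseline assessment appointment with study personnel on Zoom". That visit includes "administration of any remaining behavioral health measures". Section 4 puts baseline after enrolment and before the intervention.
- **Section 17.** In a sentence that also covers alcohol use, PTSD and depression, "suicidal risk, anxiety, and insomnia will be assessed at screening, baseline, and one-month follow-up assessments".
- **Section 6.** P-4 high risk is not among the exclusions. The third exclusion covers psychiatric impairment that needs emergency or inpatient care, and names no instrument.

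**The concern.** The P-4 rule is a safety exclusion, and a reader of Section 17 would take it that every subject's suicide risk is known before eligibility is decided. The stop rule in Section 9 does not secure this. A subject who qualifies on alcohol alone can pass through screening, consent and enrolment without being asked the one item that opens the P-4. The baseline visit is scheduled separately, and no maximum interval to it is stated. Section 2 describes this population as having more suicidal thinking and more lifetime attempts than the general population, so the timing of the check matters.

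**Working it through.** The plan gives no figure to reproduce. The check is a trace of the procedure, and it needs no assumed rate.

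**Path of an AUD-positive subject, on the order listed in Section 9**

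1. Demographic survey.
2. AUDIT of 16 or more, with past-30-day drinking above the low-risk limit. This alone meets inclusion criterion 4 in Section 6.
3. The stop rule applies. PHQ-9, GAD-7, PCL-5 and ISI are skipped and the treatment-engagement questions follow.
4. If not in treatment, the subject is eligible, is invited to written consent and is enrolled (Sections 4, 8 and 9).
5. Baseline visit: the PHQ-9 is given for the first time. Item 9 is asked and the P-4 becomes possible.
6. First CBT-TS session.

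**When item 9 is asked**

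| | Screening | Baseline | Follow-up | Enrolled before item 9? |
|---|---|---|---|---|
| AUD-positive | no | yes | yes | yes |
| AUD-negative | yes | no | yes | no |
| Section 17's schedule | yes | yes | yes | no |

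Neither group follows Section 17. Each subject meets item 9 once before the intervention, because a measure given at screening is not among those left for baseline.

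**Dependence on the order.** Section 9 refers to a list called Sources of Research Materials, which is not in the text supplied. Three cases:

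- Order as in Section 9's prose: the table applies.
- PTSD before depression, as in the disorder lists of Sections 1, 5, 6 and 17: PTSD-positive subjects would also skip item 9 at screening.
- PHQ-9 first: the AUD gap closes, but nobody would answer item 9 at baseline, so the mismatch with Section 17 remains.

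The disorder lists put alcohol before depression, but they are not administration orders. The adverse-event text in Section 17 names alcohol last, in a description of symptoms.

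**Size, under assumptions only.** The documents give no AUD share and no P-4 rate. Suppose 5 to 18 of 45 subjects (11% to 40%) screen positive for AUD, and 2% to 10% of those are P-4 high risk.

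- Expected number found only after enrolment: 5 × 0.02 = 0.1 to 18 × 0.10 = 1.8.
- Chance of at least one: 1 − 0.98^5 = 9.6% to 1 − 0.90^18 = 85.0%.

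This range is too wide to inform a decision.

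**Aim 1.** Section 7 expects 73% of those screened to be eligible: 45/0.73 = 61.6, so 62 screened. If k high-risk subjects are found at baseline and replaced, eligibility depends on how they are counted:

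- k = 1: 45/63 = 71.4% or 46/63 = 73.0%, a difference of 1.6 points.
- k = 2: 45/64 = 70.3% or 47/64 = 73.4%, a difference of 3.1 points.

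The 95% half-width for 73% of 62 is 1.96 × √(0.73 × 0.27/62), about 11 points. The counting effect is small beside it.

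**The case against.** The strongest reply is that the check still comes before exposure. Sections 4 and 9 put baseline, with every outstanding measure, ahead of any CBT-TS session, and Section 11's response (support, contact with the PI, safety planning, referral) applies whenever high risk is found. This stands. A reader might infer that high-risk subjects could receive the intervention unchecked; the documents do not support that.

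A reader might also infer that screening has no protection against suicide risk. That is too strong. The third exclusion in Section 6 bars imminent danger, screening is live with trained staff, and Section 17 requires action at any time that a danger to self is identified. These narrow the gap. They do not close it, because none ties a suicide-risk question to the screening visit.

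Third, Section 17's sentence covers six domains and could be read loosely, as one battery spread over two visits. The stop rule makes it imprecise for the other domains too. For a safety exclusion, though, the looser reading leaves some subjects with no check before enrolment, which the sentence does not convey.

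Finally, the administration order rests on a list that is not in the text supplied. That limits the AUD-specific part of the point. It does not affect the screening-and-baseline mismatch.

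**Conclusion.** The point holds as an inconsistency in a safety procedure. On Section 9's listed order, AUD-positive subjects are found eligible and enrolled before item 9 and the P-4 exclusion are applied, and on any order the schedule in Section 17 is not met at both pre-intervention visits. Section 6 does not list the exclusion. Section 15 gives only significant distress as a ground for removal, so the handling of a subject found high risk at baseline is not spelled out.

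The check is one visit late for some subjects; it is not missing. How many are affected cannot be derived from the documents. It would also be tempting to read this as a bias in the feasibility percentages or in the effect estimates. The documents do not support that: the Aim 1 differences are negligible, Section 15 replaces removed subjects, Section 17 has reasons for missing data reported, and no effect on Aim 2 is claimed. The case for change is that a cheap edit makes the suicide-risk check happen when the safety plan says it does.

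**What to change.** - **Section 9.** At screening, ask PHQ-9 item 9 of every subject before eligibility is declared, whatever the stop rule, with the P-4 if it is endorsed. Repeat item 9, again with the P-4 if endorsed, at baseline for all subjects. Section 17 then becomes true for suicidal risk as written.
- **Section 6.** Add an exclusion: high risk on the P-4 Screener at screening or baseline.
- **Section 11b.** State that a high-risk score after the intervention has started triggers the safety response and not exclusion.
- **Verbal screening consent (Section 8).** State the confidentiality limits that apply to suicide risk. Item 9 would now be asked of everyone before the written consent that explains them.

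The cost is one repeated item per subject, the P-4 where item 9 is endorsed, and a short amendment. No visits or staff are added. Simply moving the PHQ-9 to the front of the screening order is a weaker fix: baseline gives only the measures not yet done, so the PHQ-9 would drop out of baseline for everyone and Section 17's baseline check would be lost. Only listing the exclusion in Section 6 and rewording Section 17 would remove the contradiction, but would leave the check after enrolment for AUD-positive subjects.
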